7.4. Case Report Forms

All assessments and observations throughout the investigation for each subject must be carefully recorded in an electronic CRF (eCRF), or an application (Clinical Trial App) in a provided phone for each subject. Details about data capture can be found in section 11.

CRFs will be filled in by the investigator and/or delegated site personal, who have signed the Site Personnel Signature and Delegation List and Clinical Investigation Training Log. If eCRFs are used delegated site personal will be required to complete e-learning prior to system access. Delegated personal will receive credentials.

7.5. Concomitant treatment

Subjects may not be given chemotherapy or radiation treatment for two months prior to or while participating in the investigation.

Subjects may not receive or have within the past month received systemic steroid or local treatment in the peristomal area and other areas of the skin tested.

The subjects can use ring or paste as they normal do during the study. But they are not allowed to use barrier creams or similar that affect the skin/adhesive interface under the tapes.

The subject may not use concave baseplate.

7.6. Supplementary materials and equipment

The Sponsor will provide the Principal Investigator, or delegate with supplementary materials for this investigation. Supplementary materials would be:

- Computer with access to eCRFs
- Smartphones with Clinical Trial app.

8. Risk – benefit analysis and ethical considerations

The clinical investigation is conducted in accordance with current law and applicable standards see section 15. The rights, safety and well-being of human subjects shall prevail over interest of science and society.

The intended purpose of the test products is to support the rim of the ostomy base plate by providing additional adhesion to the intact peristomal skin. It is known from previous Coloplast market research that up to 40% of people with stoma worry about leakage. This potentially influences their health-related quality of life negatively. The use of ostomy tapes may reduce the worry for leakage episodes. This study will investigate newly developed ostomy tapes and their ability to adhere to the skin without affecting it. Potential benefits are that subjects can worry less for leakage episodes without affecting their skin.

No risks are expected to the subjects other than the adverse events mentioned in section 17, all of which are well known in connection with the use of ostomy tapes. The risk assessment of the test products is carried out in accordance with the requirements of ISO 14971. There is no known interaction between the use of ostomy tapes and the medication subjects can take – except from what is stated in the exclusion criteria. Disadvantages of testing may be the time spent on visits and responding questions regarding product change.

Risks have been proven minimized or eliminated through appropriate design control, confirmed by pre-clinical bench, laboratory and biological safety evaluations. Therefore, the risks are considered to be equal to the use of ostomy tapes already on the market. Risks associated with the use of ostomy tapes are skin irritation and mechanical trauma.

To mitigate and reduce the risks, the subjects will be trained, according to the IFU, in application of product (e.g. correct position), removal of product and storage of the product.

The outcome of this investigation will contribute with important information for development of products for subjects with a stoma.

Disadvantages during the investigation could be the extra workload related to completion of questionnaires, or visits at Coloplast A/S and using the clinical trial app at each change of product.

9. Monitoring Plan

The sponsor is responsible for ensuring appropriate monitoring of the clinical investigation activities.

The monitor will be the primary contact for the principal investigator and clinical investigation site personnel.

Monitoring activities are mandatory as per good clinical practice, however the extend and depth of these activities depend on the criticality of the clinical investigation, speed of enrolment, the experience of the clinical investigation site personnel in carrying out clinical investigations and specific study designs.

For the purpose of this clinical investigation the below described monitoring procedures have been determined.

9.1.1. Initiation visit

The clinical investigation site will get an on-site initiation visit during which full training on all aspects of the clinical investigation will be provided.

9.1.2. Monitoring visit(s)

The site dedicated monitor is to ensure adherence to the clinical investigation plan, accurate data recording on the eCRFs and to monitor recruitment rates and adherence to follow-up schedules. The principal investigator shall permit and assist the monitor to carry out verification of completed eCRFs against data in the source documents.

The principal investigator can delegate tasks to his/her collaborators, however the roles and responsibilities as time period of involvement for each clinical site personnel must be documented on the delegation log as well as training received before getting involved with the clinical investigation must be documented in the training log.

The monitor shall inform the sponsor about any problems relating to facilities, technical equipment or medical staff at the clinical investigation site. During the clinical investigation, monitors shall check that appropriate written informed consents have been obtained. The monitor shall also be responsible for notifying such deficiencies in writing to the principal investigator and convene with the clinical investigation site personnel appropriate and timely corrective actions.

The sponsor, or delegate, will provide clinical monitoring, including review of eCRF with verification to the source documentation, as defined in the monitoring plan.

The monitor shall make written reports to the sponsor, after each visit and provide written action items if any, to the principal investigator or clinical investigation site personnel.

9.2. Source data verification

A source document is a document in which data collected for a clinical trial is first recorded. This data is usually later entered in the electronic case report form (eCRF). Source documents are defined as "original documents,

data, and records. Source documents contain source data, which is defined as all information in original records and certified copies of original records of clinical findings, observations, or other activities in a clinical trial necessary for the reconstruction and evaluation of the trial.

All documents and data related to the clinical investigation handled by site personnel, shall be produced and maintained in a way that assures reliability, integrity, control and traceability, and shall be appropriately stored to provide a complete history.

The Principal Investigator shall assure the accuracy, attribution, completeness, legibility and timeliness of the data reported to the sponsor in the eCRFs and in all required reports. All printed copies of electronic source documents shall be certified, as indicated by a dated signature by the investigational site personnel at the time the document is printed. Special requirements should be applied to the capture, review and retention of electronic source data, to ensure reliability, quality, integrity and traceability.

The data reported in the eCRFs shall be derived from source documents and be consistent with these source documents, and any discrepancies shall be explained in writing. In some cases, the eCRF can serve as the source document and this must be documented on the Source Data Specification Form. The Source Data Specification Form must be completed at the initiation visit detailing the location of the source data for each data point.

10. Statistical considerations

10.1. Statistical design, method and analytical procedures

Definition of analysis populations

Intention to Treat (ITT) and Safety populations will be defined at a formal data review meeting just before database lock. As a minimum, the data manager, the clinical manager and the statistician will be involved in the classification of subjects.

The ITT population (full analysis set) will be constituted by all included subjects who:

- Have provided valid informed consent
- Have measurements for at least one of the endpoints or assessments

The Safety population will constitute by subjects who have given informed consent.

All statistical analysis and summaries will be based upon the ITT population whereas adverse events and Device deficiencies will be assessed based on the safety population. Invalid individual data points may be omitted from analysis even though the corresponding subject is part of the ITT population. Any exclusion of data points will be documented.

A formal PP population is not planned due to the explorative nature of the investigation.

Analysis of endpoints, individual questions and baseline data

All endpoints and individual questions as well as baseline/demographic data will be listed and summarized by descriptive statistics. The summaries for the endpoints and individual questions will be made for each product separately.

To explore potential indications of differences in adherent area the following analysis will be performed, if relevant. Adherent area can be analysed by a mixed repeated measures model using mean of the two adherent areas for each individual baseplate change as the observational unit. The model will consider that observations corresponding to different subjects are independent; whereas observations corresponding to the same subject are correlated. The correlation between observations corresponding to the same product can be larger than observations corresponding to different products. Hence the model includes a fixed effect of product (comparator product, test product A, test product B), a fixed period effect (period 1, 2, 3), a random effect of subject and a random interaction effect of product and subject. The model might be reduced by removing non-significant fixed effects, if relevant. All combinations of differences between the three products will be estimated.

Erythema measured by end of each period can be analysed by a linear mixed model like the model for the adherent area, as there is 3 measurements per subject for each product.

As it is an exploratory study no adjustment for multiple testing will be applied.

Other summaries and analyses can be made, if relevant.

All statistical analyses and summaries are made with SAS version 9.4 (SAS Institute Inc., Cary, NC).

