5.1. General

This investigation is a randomised, open-label, comparative, cross-over study, with three test periods.

In total, 12 subjects will be included and randomised, and each subject will have an inclusion visit and four test visits overseen by the Principal Investigator, or delegate. Each subject will be enrolled for three times 7-9 days in total for the entire investigation, thus for a maximum of 27 days – equal to at least 3 baseplates + tape change in each period. The subjects will test two new recipes of ostomy tapes and a comparator product in randomised order.

Between the test visits, the subjects will change products at home. At each product change, subjects will take a photo of the peristomal skin using a smartphone with a specially designed Clinical Trial app installed. Furthermore, they will answer questions about feeling of security, adhesion of tape, comfort and potential skin issues.

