5.3. Secondary endpoints

- Erythema measured after each treatment period by spectrophotometric method
- Erythema measured after tape removal by photos
- Feeling of security:
 - How was the feeling of security while wearing the tape?
(5-point scale from Very poor to Very good)
 - Did you feel confident that the tape would keep your base plate securely in place?
(5-point scale from Very little to Very much)
- Adhesion of tape:
 - How was the immediate adhesion to the skin?
(5-point scale from Very poor to Very good)
 - Did the edge of the tape lift/roll during use?
(5-point scale from Very poor to Very good)
- Comfort:
 - How comfortable was the tape to wear?
(5-point scale from Very uncomfortable to Very comfortable)
 - Did the tape allow you freedom of movement?
(5-point scale from Very little to Very much)
- Skin issues in the area covered by the tape:
 - Do you experience any **bleeding from the skin** under the tape right now when changing your product? (Experiencing/Not experiencing)
 - Once you have cleaned and dried the skin, do you experience any **weeping or moisture on the skin** under the tape right now when changing your product? (Experiencing/Not experiencing)
 - Are you experiencing any **ulcers or sores** under the tape right now when changing your product? (Experiencing/Not experiencing)
 - Did you experience complications where the tape was applied (like pain, stinging, itching, heat swelling or shiny skin)? (Yes/No)

- Please rate how painful the skin under the tape has been at its worst, since you last changed your product. (10-point scale from no pain (1) to worst pain possible (10))
- Please rate how itchy the skin under the tape has been at its worst, since you last changed your product. (10-point scale from no itch to worst itch possible)
- Adverse events

User experience with feeling of security, adhesion of tape, comfort and skin issues in the area covered by tape, will be assessed by prior mentioned questionnaires which will be assessed by interviews at Coloplast visit and self-reported by user at home.

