7.2. Visits

Baseline visit (V0):

- Introduction to the study
- Informed Consent and letter of authority signed
- Check of in- and exclusion criteria
- Visual evaluation of skin for inclusion
- Pregnancy test - dipstick (for women of child-bearing potential only)
- Inclusion in study and allocation of subject number
- Collect baseline information
- Possibility to accept interview by User Insight/development engineers/project members

Test visit 1:

- Randomisation
- Instruct subject in use of smartphone and Clinical Trial app and remind the subject to bring it for every study visit
- Remove tape/product with use of adhesive remover
- Photo of peristomal skin (digital camera)
- Acclimatization of peristomal skin for ½ hour
- Photo of peristomal skin after acclimatization (digital camera)
- Measurements of erythema
- Provide randomized test products or comparator products for the subject for change at home and apply 2 ostomy tapes on the peristomal skin (after ostomy product has been applied).
- Provide storage material for used ostomy tapes and adhesive remover
- Instruct and remind the subject to follow the study specific procedures between visits
- Schedule next visit in 7-9 days

Test visit 2 and 3:

- Follow up on subjects use of smartphone and Clinical Trial app and remind the subject to bring it for every study visit
- Ostomy tapes are removed with use of adhesive remover (before removing, mark the lifted tape area with a pen on the adhesive part)
- Photo of peristomal skin (digital camera)
- Photo of skin (smartphone – Clinical Trial App)
- Smartphone: Questionnaire about feeling of security, adhesion of tape, comfort & skin issues in the area covered by the tape
- Acclimatization of peristomal skin for ½ hour
- Photo of peristomal skin after acclimatization (digital camera)
- Measurements of erythema

- Provide randomized test products or comparator products for the subject for change at home and apply 2 ostomy tapes on the peristomal skin (after ostomy product has been applied).
- Provide storage material for used ostomy tapes and adhesive remover
- Instruct and remind the subject to follow the study specific procedures between visits
- Schedule next visit in 7-9 days
- Collect all used tapes and measure the adherent area
- Review AEs/ADEs/SAEs/SADEs
- Possibility to accept interview by User Insight/development engineers/project members

Termination visit 4:

- Follow up on subjects use of smartphone and Clinical Trial app

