7.3. Flow-chart

Table 3 chart showing the connection between visits and assessments.

	PERFORMED BY	BASELINE	TEST PERIOD	TEST PERIOD	TEST PERIOD	TERMINATION
VISIT WINDOW (DAYS)	-	-	-	7 - 9	7 - 9	7 - 9
GENERAL						
Subject information	Investigator	X				
Signed informed consent	Subject / Investigator	X				
Signed letter of authority	Subject / Investigator	X				

Allocation of subject number	Investigator	X				
Check of in- and exclusion criteria	Investigator	X				
Visual evaluation of skin for inclusion	Investigator	X				
Pregnancy test, dipstick (If applicable)	Investigator	X				
Randomization	Investigator		X			
Insurance of subjects' wellbeing and compliance with CIP	Investigator	X	X	X	X	X
COLLECTION AND REGISTRATION OF BASELINE DATA						
Demographics: Gender, age, height and weight	Investigator	X				
Stoma: Type, reason and duration	Investigator	X				
Use of ostomy tape (Y/N)	Investigator	X				
Use of other accessories (Ring and paste)	Investigator	X				
Usually stoma product used	Investigator	X				
Optionally interviews	Development engineers/project members			X	X	X
PROCEDURES						
Instruct in and follow up on subjects use of smartphone and Clinical Trial app	Investigator		X	X	X	X
Remind the subject to bring the smartphone at every study visit	Investigator		X	X	X	X
Mark the lifted tape area with a pen on the adhesive part, before removing the ostomy tapes	Investigator			X	X	X
Remove tape/product with use of adhesive remover.	Investigator		X	X	X	X
Photo of peristomal skin (digital camera)	Investigator		X	X	X	X
Photo of peristomal skin (smartphone)	Subject			X	X	X
Acclimatize peristomal skin for ½ hour	Subject		X	X	X	X
Smartphone, Questionnaire: Feeling of security, adhesion of tape and comfort	Subject			X	X	X
Smartphone, Questionnaire: Skin issues in the area covered by the tape	Subject			X	X	X
Photo of peristomal skin, after ½ hour acclimatization (digital camera)	Investigator		X	X	X	X
Measure erythema	Investigator		X	X	X	X
Provide test products to the subject	Investigator		X	X	X	
Apply ostomy product and ostomy test tapes (Test tapes should be applied at the edges of the baseplate)	Subject		X	X	X	
Provide storage material for used ostomy tapes and adhesive remover	Investigator		X	X	X	
Instruct and remind the subject to follow the study specific procedures between visits	Investigator		X	X	X	X

Schedule next visit	Investigator	X	X	X	X	
Collect all used tapes and measure the adherent area by photography	Investigator			X	X	X

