10.2. Sample size

Due to the conceptual nature of this trial (pilot evaluation of ostomy tapes under development) no formal sample size calculation has been performed. The evaluation will be supported by data from laboratory models. Twelve subjects are expected to provide enough information for further adjustment of the recipe.

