10.3. Level of significance and power

If a statistical analysis is performed a two-sided significance level of 5% will be applied. As this is an exploratory study no power has been applied.

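### With no washout and no rule to separate new from persisting skin findings, a lesion from one tape can also be counted against the next

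*Combined protocol and SAP*

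**What the plan says.** Section 5.1 gives the design: "This investigation is a randomised, open-label, comparative, cross-over study, with three test periods". On duration it says: "Each subject will be enrolled for three times 7-9 days in total for the entire investigation, thus for a maximum of 27 days".

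At Test visits 2 and 3 (Section 7.2) the old tapes come off, and the skin photos and questionnaire follow. The skin then rests for half an hour and erythema is measured. At the same visit the next product is supplied, with the step "apply 2 ostomy tapes on the peristomal skin (after ostomy product has been applied". The closing questionnaire is therefore answered before the new tape goes on and belongs to the old one.

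In Section 5.3 the bleeding, weeping/moisture and ulcer/sore items share the wording "under the tape right now when changing your product? (Experiencing/Not experiencing". Pain and itch instead ask about the worst since the last change. Erythema is assessed on photos after tape removal, and by instrument after each period.

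For analysis, Section 10.1 says: "The summaries for the endpoints and individual questions will be made for each product separately". Its mixed model has product, period, subject and product-by-subject terms, with no carry-over term and no start-of-period value. It is specified for adherent area and, in similar form, for erythema at period end, not for the skin questions. In the flow-chart (Section 7.3), "Visual evaluation of skin for inclusion" is ticked at baseline only, while digital skin photos are ticked at every test visit.

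**The concern.** The three items record presence, not onset. Take a subject who reports a sore at visit 2, at the end of the first product. If the sore is still there at the first home change under the second product, the answer is again positive. On the natural reading of Section 10.1 it is summarised under the second product. Nothing in the planned summary distinguishes it from a sore that the second product caused.

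The secondary objective is the state of the skin after each tape, and Section 10.2 expects the results to guide further adjustment of the recipe. A tape that follows an irritating one can look worse than it is, which makes the irritating one look relatively better. In a table based on 12 subjects, a single misattributed sore is visible.

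**Working it through.** **Room for a washout.** 3 periods × 9 days = 27 days. This reproduces the stated maximum exactly and leaves 0 days between periods.

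**Which products follow another study tape.** Inputs are the six arms in Section 5.6, 12 subjects and blocks of 6. I assume that each block holds each listed arm once, so there are 2 subjects per arm. With C for the comparator, the arms are ABC, BAC, CAB, CBA, BCA, BAC. Arms 2 and 6 coincide, and the order A, C, B is absent.

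| Product | First (nothing before) | Preceded by | Total preceded |
|---|---|---|---|
| A | 2 | B 6, C 4 | 10 of 12 |
| Comparator | 4 | A 4, B 4 | 8 of 12 |
| B | 6 | A 4, C 2 | 6 of 12 |

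That makes 24 switches, so 24 of the 36 subject-periods start on skin that has just carried another study tape.

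**Effect on the summary when the tapes are identical.** Let p be the true prevalence per record. Let r be the number of next-period records affected for each own-period record affected. To first order, ignoring overlap of old and new findings:

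summarised prevalence = p × (1 + r × preceded/12)

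Neither p nor r is given. I take p = 10%. The nearest figure, under 10% for skin irritation in Section 17.2, is an incidence ceiling and not a per-record prevalence. I also assume that successive tapes cover the same skin.

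For r, take changes on days 2, 4, 6 and 8 and a finding that lasts about a week, that is, four consecutive records. If onset is equally likely at each change, own-period records are 4, 3, 2, 1 (mean 2.5) and next-period records are 0, 1, 2, 3 (mean 1.5). So r = 1.5/2.5 = 0.6.

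| r | A | Comparator | B |
|---|---|---|---|
| 0 | 10% | 10% | 10% |
| 0.25 | 10 × (1 + 0.25 × 10/12) = 12.1% | 10 × (1 + 0.25 × 8/12) = 11.7% | 10 × (1 + 0.25 × 6/12) = 11.3% |
| 0.6 | 10 × (1 + 0.6 × 10/12) = 15% | 10 × (1 + 0.6 × 8/12) = 14% | 10 × (1 + 0.6 × 6/12) = 13% |

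The false A-minus-B gap is p × r × (10 − 6)/12 = p × r/3, which is 2 points at r = 0.6. With 12 × 4 = 48 records per product, that is 0.02 × 48 = 0.96, or about one record.

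**Six distinct orders.** Every product would be preceded in 8 of 12 subjects, so identical tapes would be inflated equally. A true A-minus-B difference would be multiplied by 1 − r/3, that is, 0.92 at r = 0.25 and 0.80 at r = 0.6.

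**Counting subjects when only A causes sores.** Use p = 10% per subject and let q be the chance that a sore persists into the next period. A is charged with 12 × 0.10 = 1.2 expected subjects. B follows A in 4 subjects, which gives 4 × 0.10 × q. The comparator gets the same, plus 2 × 0.10 × q² from the two subjects on Arm 1.

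| q | A | B | Comparator |
|---|---|---|---|
| 0.25 | 1.2 | 0.10 | 0.11 |
| 0.5 | 1.2 | 0.20 | 0.25 |
| 1 | 1.2 | 0.40 | 0.60 |

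**The case against.** The strongest reply is that this is a descriptive secondary summary in a pilot. Section 10.2 says "no formal sample size calculation has been performed", Section 10.3 says "As this is an exploratory study no power has been applied", and Section 10.4 sets no pass/fail criteria. All answers are listed as well as summarised, so a persisting sore can be traced by hand in 12 subjects. Skin photos are taken at every test visit, adverse events are registered, and Section 10.1 allows other summaries if relevant. This stands as a limit on the consequence. It does not supply an attribution rule, and one chosen after the results are seen is weaker.

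Four stronger readings are tempting but unsupported.

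- A reader might infer that a lesion is always counted twice. It must still be present, under the new tape, about two days or more after the switch. The documents do not say how long lesions last or whether tape sites coincide.
- A reader might extend the point to all redness. No present-state question asks about redness, the instrument is read 7-9 days after the switch, and Section 17.2 treats redness on removal as temporary. Only lasting redness is exposed, through the photos.
- A reader might take a week-long finding to occupy three of the next four changes. That holds only if it starts at the closing visit.
- A reader might infer that skin is looked at only at baseline. The photos and closing questionnaires at visits 2 and 3 record its state before each switch. The gap is that Section 10.1 does not use them.

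**Conclusion.** The point holds as a possibility that the plan leaves uncontrolled, not as a demonstrated bias. The documents establish the same-visit switch, the present-state wording of three items, and the absence of any rule for inherited findings. The size rests on assumptions about persistence, site overlap and a 10% prevalence. It runs from nothing at r = 0 to a 2-point false gap between A and B at r = 0.6, and it scales in proportion to p.

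The missing washout by itself does not create a difference between identical tapes. The unequal part comes from the repeated sequence in Section 5.6. Without that repetition, true differences would still be diluted, by about 8% to 20% for r of 0.25 to 0.6. Pain and itch are less exposed because of their recall window. The change is worth making because it is nearly free and serves the secondary objective.

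**What to change.** In Section 10.1, keep the planned all-records summary by product and add the following.

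- **Bleeding, weeping and ulcer/sore items:** a summary split by the last record before that product's first tape. That record is the closing questionnaire at visit 2 or 3, or the entry skin evaluation for period 1. Report new findings among subject-periods negative at the switch, with that number as the denominator. Show findings already present at the switch separately.
- **Photo erythema:** keep all changes, add a summary of the closing record of each period, and show period 1 alone as a sensitivity summary.
- **Pain and itch:** leave as planned.

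The denominator matters. Suppose that identical tapes irritated every subject through to period end. Only first-period findings would count as new, giving A 2/12, comparator 4/12 and B 6/12 on the full sample, a false threefold spread. Among those at risk the figures are 2/2, 4/4 and 6/6.

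No new visit procedure is needed. The cost is one extra table for the three items, with small denominators, and the short erythema summaries. Worsening of an inherited lesion would not count as new, so the raw answers should stay listed. The repeated sequence in Section 5.6 needs reconciling in its own right. Six distinct orders would equalise the carry-over but not remove it.

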- Ostomy tapes are removed with use of adhesive remover (before removing, mark the lifted tape area with a pen on the adhesive part)
- Photo of peristomal skin (digital camera)
- Photo of skin (smartphone – Clinical Trial App)
- Smartphone: Questionnaire about feeling of security, adhesion of tape, comfort & skin issues in the area covered by the tape
- Acclimatization of peristomal skin for ½ hour
- Photo of peristomal skin after acclimatization (digital camera)
- Measurements of erythema
- Application of stoma product which subject normally use
- Collect all used tapes and measure the adherent area
- Review AEs/ADEs/SAEs/SADEs
- Collect smartphone
- Possibility to accept interview by User Insight/development engineers/project members
- Fill in termination form

Product change and study specific procedures, to be followed at home:

Between visits the subject will change at home. At each product change, the subject should record experience at home by taking photo of the peristomal skin and answer questionnaires (with a Clinical Trial app on a handed-out smartphone).

At home:

- a) Remove tape with use of adhesive remover (before removing mark the lifted tape area with a pen on the adhesive part).
- b) Remove the tape from baseplate and save the tapes in the provided storage material for the next visit
- c) Take photo of peristomal skin.
- d) Answer questions (about feeling of security, adhesion of tape, comfort & skin issues in the area covered by the tape)

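### Section 10.1 plans no within-subject product comparison for the questionnaire items and, as best read, photo-scored erythema, although the study is a crossover

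*Combined protocol and SAP*

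**What the plan says.** Section 5.1 describes the design: "This investigation is a randomised, open-label, comparative, cross-over study, with three test periods". Each subject is meant to use test product A, test product B and the comparator in turn, for 7 to 9 days each.

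Section 5.3 lists the questionnaire items: six 5-point items on security, adhesion and comfort, four yes/no skin items, and 10-point ratings of pain and itch. It also lists erythema twice, once by instrument after each period and once from photos after tape removal. Most of these data recur within a period. Section 7.2 says of the home procedures: "At each product change, the subject should record experience at home by taking photo of the peristomal skin and answer questionnaires".

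On analysis, section 10.1 says "All endpoints and individual questions as well as baseline/demographic data will be listed and summarized by descriptive statistics", and then "The summaries for the endpoints and individual questions will be made for each product separately".

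A model is named for two outcomes only:
- **Adherent area**, which is itself measured from photos, may be analysed by a mixed model. It has fixed product and period effects and random subject and subject-by-product effects, and all pairwise product differences are to be estimated.
- **Erythema at the end of each period** may be analysed by a similar model.

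The section closes by leaving room for further unspecified analyses.

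**The concern.** In a crossover the informative quantity is each subject's own difference between products. Section 10.1 recognises this for adherent area, where it states that values from one subject are correlated and builds that into the model. It gives no reason for leaving it out for the questionnaire items, which come from the same subjects, periods and tape changes.

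The skin items and photo-scored erythema bear directly on the secondary objective, the state of the skin after use. If they reach the report only as three separate columns, a reader can compare products only by eye, between columns. Large differences between subjects then obscure the product contrast, the columns need not contain the same people, and no allowance is made for period.

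A lesser matter is the unit. The section does not say whether a product summary counts tape changes or subjects.

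**Working it through.** **Figures in the plan.** There is no precision figure to reproduce. Section 10.2 says "no formal sample size calculation has been performed" and section 10.3 says "As this is an exploratory study no power has been applied". The stated duration agrees with itself: 3 × 9 = 27 days.

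**Which outcomes lack a within-subject analysis.** Setting section 5.3 against section 10.1, none of the twelve questionnaire items has a model or paired display. Photo-scored erythema is less certain. The end-of-period wording of the erythema model matches the instrument endpoint, but its remark about three measurements per subject and product would fit repeated photos better. The instrument reading is the better one, so photo-scored erythema is most likely left with per-product summaries.

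**Precision.** Inputs: n = 12 (section 5.1), and a correlation ρ between a subject's values on two products. The documents give no ρ, so 0.3 to 0.7 is an assumption. With one value per subject and product, and standard deviation σ:
- unpaired SE = σ√(2/12) = 0.408σ
- paired SE = σ√(2(1 − ρ)/12)

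| ρ | paired SE | unpaired ÷ paired = 1/√(1 − ρ) |
|---|---|---|
| 0.3 | 0.342σ | 1.20 |
| 0.5 | 0.289σ | 1.41 |
| 0.7 | 0.224σ | 1.83 |

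**Incomplete data.** Withdrawn subjects are not replaced (section 6.3). The ITT set needs a measurement on only one endpoint or assessment, and individual values judged invalid can be left out (section 10.1). Illustration: eleven subjects rate 4 on every tape, and one rates 1 but has no data for tape A. The separate means are 4.00 for A and (11×4 + 1)/12 = 3.75 for the comparator, a gap of 0.25. Yet every within-subject difference that can be observed is zero.

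**Period.** In section 5.6 as written, Arms 2 and 6 are the same sequence and the order A, comparator, B is absent. Mean period over the six arms:
- B: (2+1+3+2+1+1)/6 = 1.67
- A: (1+2+2+3+3+2)/6 = 2.17
- Comparator: (3+3+1+1+2+3)/6 = 2.17

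Unadjusted summaries would therefore carry 2.17 − 1.67 = 0.5 of any linear per-period trend into comparisons with B.

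**Summary unit.** Section 5.1 expects a number of changes "equal to at least 3 baseplates + tape change in each period". Section 6.1.1 allows changes no more often than every second day, so 7 to 9 days give at most 3 to 4. If records were pooled:
- Six subjects with 3 changes and six with 4, the two groups one point apart: shift = (4/7 − 1/2) × 1 = 0.07.
- Eleven subjects with 3 changes rating 4 and one with 4 changes rating 1: record mean (33×4 + 4×1)/37 = 3.68, against a subject mean of 3.75, a gap of 0.07.

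The eligibility criterion sets no upper limit on wear. A 3-day wear in a 7-day period gives only 2 changes, which does not meet the minimum in section 5.1, so the two sections should be reconciled. If half the subjects made 2 changes and half 4, the first shift would be (4/6 − 1/2) × 1 = 0.17.

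**The case against.** This is a 12-subject pilot meant to guide recipe adjustment, with no pass/fail criteria, and testing is conditional: "If a statistical analysis is performed a two-sided significance level of 5% will be applied". Descriptive summaries of user-experience questions are a defensible choice in that setting. Means, linear models and many unadjusted intervals on 5-point items in 12 people are not beyond criticism either. This stands as a reason to label the added analyses exploratory. It does not explain why a study described as comparative and crossover plans no comparison for these items.

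Four stronger readings are tempting, and the documents do not support them:
- *The crossover information is discarded.* It is not. Individual data are listed and further analyses are allowed. With complete data and one value per subject and product, the difference in product means is the same paired or unpaired. The plan simply does not plan the within-subject comparison, and permission for other analyses commits to none.
- *All photo endpoints lack a model.* Adherent area is photo-based and has one.
- *Frequent changers dominate the summaries.* The plan is silent on the unit. It permits pooling but does not state it, and within 3 to 4 changes the effect is trivial.
- *The standard-error ratio measures a loss in an analysis the plan proposes.* The plan names no interval or test for these items. The ratio shows what pairing could offer, under an assumed correlation.

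**Conclusion.** The concern holds in a limited form. For the questionnaire items, and most likely photo-scored erythema, section 10.1 states a weaker method than the design supports and than it offers for two other outcomes.

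The possible gain in precision is a factor of about 1.2 to 1.8 in the standard error, resting wholly on an assumed correlation of 0.3 to 0.7. Two further weaknesses do not depend on that assumption: separate summaries can cover different subjects when data are missing, and they carry period effects if the arm list is used as written. How large either would be cannot be known from the documents.

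The undefined summary unit is secondary, at about 0.07 points in the examples. The primary endpoint is not affected. This is a cheap improvement to the secondary analyses, not a flaw that undermines the study.

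**What to change.** In section 10.1:
1. Keep the per-product summaries, but base them on one value per subject and product: mean or median over changes for scaled items, any/none for yes/no items.
2. Add exploratory within-subject differences (A − comparator, B − comparator, A − B) with 95% intervals, or the adherent-area mixed model with its period effect where the scale allows. Prefer the model, with period retained, if the arm list in section 5.6 is used as written, because simple paired differences do not remove the period imbalance.
3. For yes/no items, show paired subject counts for each pair of products: yes on both, on the first only, on the second only, on neither.
4. State which erythema endpoint the end-of-period model covers, and treat photo-scored erythema in the same way as the items above.

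The cost is some SAP wording and a few more tables, with no new data. The downside is a set of unadjusted exploratory intervals on ordinal items in 12 subjects, which should be labelled as such.
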